8.5.2 Information about risks and benefits and informed consent

Women will be informed of possible benefits and known risks by means of a generic prolapse surgery consent form, discussion with the local Recruitment Officers and their own gynaecologist. Women who are not able or not willing to give informed consent to be studied will not be recruited.

9. FINANCE

The study is supported by a grant from the NIHR Evaluation, Trials and Studies Coordinating Centre (NETSCC), Health Technology Assessment (HTA) Programme (ref 07/60/18).

10. EXPLANATORY STUDIES

The funds provided by the NETSCC HTA are to conduct the randomised controlled trials and Comprehensive Cohort study as described in this protocol. It is recognised, however, that the value of the study will be enhanced by ancillary studies of specific aspects. Plans for some of these may be submitted to other grant funding bodies. Suggestions will be discussed and agreed in advance with the TSC and also agreed with the NETSCC HTA. Appropriate legislative approvals will be sought for any new proposals.

11. INDEMNITY

The Patient Information Sheet provides the following statement regarding indemnity for negligent and non-negligent harm:

We do not expect any harm to come to you by taking part in this study. All the materials and techniques are already being used in the NHS for prolapse surgery. Your participation in the study is therefore only to help us evaluate these procedures and should not involve any additional risk to you. Taking part in this study does not affect your normal legal rights. Whether or not you do take part, you will retain the same legal rights as any other patient in the NHS (which include professional indemnity insurance for negligence). If you wish to complain about your health care or any aspects of this study, the normal NHS mechanisms will be available to you.

In addition, the universities involved with this study hold and maintain a 'no fault' insurance policy. This policy covers all employees of the universities and those working under their direction.

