3.1 Planned interventions

Women will be randomised to an operation (see Appendix I, Section 1.3) according to their surgical history (previous prolapse repair or not), the availability of the mesh (non-absorbable and/or biological) and the skill capacity of their operating gynaecologist (trained in mesh kit use or not). The study design is shown in the Flow Diagram (Appendix II).

If the non-absorbable mesh inlay or the biological mesh graft is temporarily or permanently (due to financial constraints) unavailable then the women can be randomised to one of the other two arms.

In addition, the expectation is that mesh kits would normally only be used for women who had been randomised to this option. If the operating gynaecologist is not trained in the use of mesh kits the women under their care will be randomised to one of the other two arms. Furthermore, in view of the scarcity of data about its safety and efficacy, we propose to use it only for women who are having a secondary procedure, who have a more complex prolapse problem.

Therefore, women having a primary repair may be randomised to:

- standard anterior and/or posterior repair (central plication) (reference technique);
- standard anterior and/or posterior repair with biological mesh inlay; or
- standard anterior and/or posterior repair with a non-absorbable or hybrid mesh inlay.

Women having a secondary repair may be randomised to:

- standard anterior and/or posterior repair (central plication) (reference technique);
- standard anterior and/or posterior repair with a non-absorbable or hybrid mesh inlay: or
- a mesh kit (using an introducer device) with a non-absorbable or hybrid mesh.

As different mesh types and materials are being introduced, surgeon preference, ability and availability may influence the technologies chosen. However, choices will be limited to mesh from two classes: biological mesh (primary surgery only) or non-absorbable / hybrid mesh. Mesh type and divergence from pre-specified choices will be documented with reasons. All other operative variables will be recorded or standardised using agreed protocols.

The exact operative protocols, including permitted types of mesh, will be agreed and standardised by consensus with the Research Committee of BSUG before the trial begins.

Control interventions

The women in different arms of the surgical trials will act as controls for each other (within each trial). However, the first option (standard anterior and/or posterior

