8.5 Ethical issues and arrangements

The North of Scotland Ethics Committee (NOSRES) has reviewed this study. The study will be conducted according to the principles of good practice provided by Research Governance Guidelines.

We believe this study does not pose any specific risks to individual participants beyond those of any surgery, nor does it raise any extraordinary ethical issues. It is possible that cultural or religious factors may affect the choice of graft material, as some biological grafts are of porcine origin (which may be inappropriate for certain religious groups). This will be taken into account in choosing appropriate materials for particular groups.

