1.2.2 Surgical management for women with anterior or posterior vaginal wall prolapse

A new update of the Cochrane Review of surgery for prolapse¹ identified 13 RCTs of surgical interventions for women with anterior or posterior pelvic organ prolapse. The IP review⁴ for NICE has identified a further nine RCTs which are not yet included in the Cochrane review. The total number of women receiving mesh in the IP systematic review⁴ was 4569: mesh was inserted using an introducer device, trochar or kit in 503 of these women. There were no data on the differential effects in women having primary as opposed to secondary surgery: all the trials reported both groups of women together despite their potentially different prognoses.

Differences in inclusion criteria or interventions (e.g. types of women, operations or mesh) precluded much useful meta-analysis or reliable conclusions. There were two small but inconclusive RCTs comparing standard repairs with or without mesh with site specific fascial defect repairs^{22;23}. There were another two small and inconclusive RCTs which included a mesh introducer device arm. ^{24;25}

For anterior vaginal wall prolapse, the limited RCT data from the Cochrane review¹ and the IP review⁴ (9 RCTs) suggested that any mesh might reduce subsequent objective anatomical relapse (77/557, 14% relapse) compared with using no mesh (179/591, 30%) (RR 0.48, 95% CI 0.32 to 0.72) in the short term. The IP review⁴ also included additional data from non-randomised comparative studies and case series. Using these extra data, non-absorbable synthetic mesh had the lowest failure rate:

- compared with absorbable synthetic mesh (OR adjusted for bias from study design 0.23, 95% CI 0.12 to 0.44);⁴ and
- compared with absorbable biological mesh (OR adjusted for bias from study design 0.37, 95% CI 0.23 to 0.59).⁴

On the other hand, the mesh erosion rates increased from 1% (95% CI 0.1% to 4%) with synthetic absorbable mesh to 6% with absorbable biological mesh to 10% with non-absorbable synthetic mesh.⁴ The data were too sparse, however, for other

reliable statistical analysis. There were insufficient data on women's subjective prolapse symptoms or complications such as infection, blood loss or dyspareunia, and none on long term outcomes. Particular safety worries are related to the use of introducer devices (trochars) that are needed for the blind insertion of mesh into intra-pelvic spaces.²⁶

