There is no evidence to suggest whether or not the use of mesh (particularly non-absorbable synthetic mesh which has the strongest mechanical strength and remains in situ indefinitely) should be reserved for more complex or recurrent prolapse. Although gynaecologists have stated that this is their belief and practice, ³⁰ evidence suggests that the majority (70%) of the current recipients of mesh are having their first prolapse operation. ⁴ An Interventional Procedures review with 503 women ⁴ and a further recent case series of 289²⁶ women drew attention to the high incidence of serious adverse effects (e.g. 2.8% with damage to surrounding organs) in women having mesh inserted with blind introducer devices. Our opinion is that until their benefits and risks have been properly evaluated, mesh kits using non-absorbable synthetic mesh should be reserved for more complex cases of prolapse. Therefore we will limit this option to women being treated for a recurrence of prolapse in the same site after primary surgery.

The initial purchase cost of mesh inlays (around £200 per woman) and mesh kits (around £400-600) is likely to have a significant impact on the cost of prolapse surgery. The proposed trial will provide evidence to indicate whether the extra costs of mesh are justified in terms of better outcomes for women and for the NHS.

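### For randomised women, the quoted Patient Information Sheet's assurance of no additional risk does not follow from its stated reason and conflicts with the protocol's own account of mesh and mesh kits

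*Protocol*

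**What the plan says.** Protocol section 11 (Indemnity) reproduces a statement from the Patient Information Sheet. It says that no harm is expected from taking part, and gives a reason: "All the materials and techniques are already being used in the NHS for prolapse surgery". It then concludes: "Your participation in the study is therefore only to help us evaluate these procedures and should not involve any additional risk to you". Section 8.5 makes a similar, more hedged statement: "We believe this study does not pose any specific risks to individual participants beyond those of any surgery".

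Other parts of the protocol read differently:

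- **Section 3.1**, on kits in this study: "the expectation is that mesh kits would normally only be used for women who had been randomised to this option". The same section gives the scarcity of safety and efficacy data as a reason for limiting kits to secondary repairs.
- **Summary in Plain English**: the kit is thought to be more invasive than the alternatives, and some operations may bring better cure with more complications, mesh-related ones in particular.
- **Appendix I, 1.3**: a review and a case series are cited for "the high incidence of serious adverse effects (e.g. 2.8% with damage to surrounding organs) in women having mesh inserted with blind introducer devices".
- **Appendix I, 1.2.2**: erosion rises to "6% with absorbable biological mesh to 10% with non-absorbable synthetic mesh". The section also reports guidance that mesh be used only under special arrangements.
- **Section 8.4.2**: mesh erosion is listed among the occurrences to be expected after surgery.
- **Section 8.5.1**: which operation carries more risk is not known.

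**The concern.** The assurance moves from the fact that the techniques exist in the NHS to the claim that taking part adds no risk. That step needs a further premise: that each woman would have had the same operation outside the study. Randomisation removes that premise. A woman who would have had a repair without mesh can be allocated mesh because she joined.

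What is at stake is the accuracy of a statement about risk addressed to participants. No estimate, test or monitoring rule depends on it. It still matters after recruitment, because follow-up is planned to 14 years (Appendix IV), and that appendix says adverse effects of mesh may appear many years later.

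**Working it through.** The documents give no figure for the risk of taking part, so there is none to reproduce. The check is a comparison of statements, followed by arithmetic on how many women are concerned and what can and cannot be quantified.

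**1. Does the conclusion follow?**

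- *Kits.* Section 3.1 expects kits normally to be used only after randomisation to them. For a woman allocated a kit, taking part is therefore normally how she comes to have one. Any hazard specific to the kit is then a consequence of participation, whether or not kits are used elsewhere in the NHS.
- *Inlays.* No such rule exists, and some women would have had an inlay anyway. For a woman who would not, allocation to an inlay brings a hazard that a repair without mesh cannot produce, namely erosion of that inlay.
- *Overall risk.* Section 8.5.1 says it is unknown which operation is riskier. An unknown difference does not support a statement of no difference.

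**2. How many women?** Inputs are SAP Tables 2 and 3.

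| Trial | Standard | Synthetic inlay | Biological inlay | Kit | Total |
|---|---|---|---|---|---|
| Primary | 253 + 178 + 116 = 547 | 256 + 181 = 437 | 255 + 114 = 369 | – | 1353 |
| Secondary | 24 + 31 + 1 = 56 | 24 + 28 = 52 | – | 44 + 3 = 47 | 155 |

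The totals agree with Appendix IV (1353 and 155).

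- Allocated any mesh procedure: 437 + 369 + 52 + 47 = 905 of 1508 = 60%.
- Allocated a kit: 47 of 1508 = 3.1%.

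**3. Gross counts at the protocol's rates (illustration only).**

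- Primary-trial erosions: 0.10 × 437 + 0.06 × 369 = 43.7 + 22.1 = 65.8 among 806 women allocated an inlay.
- Organ damage in the kit arm: 0.028 × 47 = 1.3 events.

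**4. Why these are not excess risks.**

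*Erosion.* Let f be the share of primary-trial women who would have had mesh outside the study and r the erosion rate with that mesh. The net expected number of erosions due to participation is 65.8 − 1353 × f × r. The documents do not give f.

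- If f = 0, the net is 65.8.
- If r = 10%, the net reaches zero at f = 65.8 / 135.3 = 49%.
- If r = 6%, it reaches zero at f = 65.8 / 81.2 = 81%.

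So even the sign of the average effect depends on an unknown. The 70% in Appendix I, 1.3 cannot stand in for f: it is the share of mesh recipients having a first operation, not the share of first operations that use mesh.

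*Organ damage.* No rate for standard repair is given. If that rate is assumed to lie between 0% and 2%, the excess with kits is 2.8 to 0.8 percentage points. It is nil if the standard rate is also 2.8%.

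**The case against.** The strongest reply has four parts.

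- **The extract is indemnity text from a sheet we cannot see.** Section 2.2 promises counselling on how little is known about outcomes and complications, especially with mesh, and a generic consent form that stresses adverse effects. Section 8.5.2 says women are told the known risks. This stands. A reader might infer that women were not told about mesh risks, and the documents do not support that.
- **The right comparison is with the surgery a woman would otherwise have had.** Appendix I, 1.3 says many gynaecologists already use mesh. This also stands. A reader might take the 66 erosions as harm caused by the trial, but they are a gross count. Offsetting benefit is left out too: Appendix I, 1.2.2 gives anatomical relapse after anterior repair of 14% with mesh against 30% without.
- **The rates are weak.** The erosion figures sit in a discussion of anterior-wall prolapse that calls the data sparse. No rate is given for combined mesh. The 2.8% has no comparator, and section 8.4.2 says these harms can also follow standard repair. This stands as a limit on size.
- **The clearest limb is small.** The kit rule concerns 47 women. That is true, but they were also given the least-tested option.

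None of this supplies the missing premise. Disclosure elsewhere does not make an unqualified assurance accurate; it leaves two messages that disagree.

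**Conclusion.** The point holds as an inaccurate assurance to randomised women. It is strongest for the 47 allocated a kit. It applies with less force to the other 858 of the 905 allocated mesh (905 − 47), some of whom would have had mesh in any case. For women in the non-randomised cohort the sentence may be true. Section 8.5 is milder, being worded as a belief, but has the same gap.

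The documents do not support a figure for excess risk, a finding of non-disclosure, or a claim that the wording changes how women report symptoms.

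The conclusion assumes that the rule on kit use in section 3.1 was followed in practice, and that the text in section 11 is what participants were given.

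**What to change.** Reconcile sections 11 and 8.5 with the Summary in Plain English, sections 3.1 and 8.5.1, and Appendix I (1.2.2 and 1.3):

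- Remove the unqualified statements that no harm is expected and that no risk is added.
- Say that allocation may be to a mesh procedure, possibly one the woman would not otherwise have had, that mesh carries risks of its own, and that the relative risk of the operations was unknown.

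Recruitment closed in August 2013, so consents already given cannot be altered. Apply the correction to any participant-facing text still in use in long-term follow-up, after ethics review and through the existing newsletters. Do not rely on the 2008 review figures for this, since Appendix IV says the trial has collected its own complication data.

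The cost is a small wording amendment and an ethics notification. More women may also ask which procedure they had. Section 2.6 allows them to be told on request, but each such answer unblinds a woman whose remaining symptom scores are self-reported. No design, analysis or clinical rule changes.

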APPENDIX I BACKGROUND TO THE STUDY

1. THE REASONS FOR THE TRIAL

Introduction

Gynaecologists have recognised for some time that both anatomical failure of supporting pelvic structures and recurrence of prolapse after surgery are common. More recently, it has also been recognised that surgery can be followed by a greater impairment of quality of life than the original prolapse itself (for example new urinary incontinence after surgery or new prolapse at a different site). Furthermore, additional surgical support materials are being actively promoted and introduced to clinical practice (including many types of mesh with different properties), without robust evidence of their value or clear analysis of the risks (such as infection, erosion or dyspareunia) from rigorous independently-managed RCTs.

This study will definitively assess which of the most frequently employed techniques for the most common types of prolapse (anterior and posterior vaginal wall prolapse) produce the optimal symptomatic result. This will guide gynaecologists in their surgical practice and purchasers in their choice of provision of health care. The study will also identify which procedures are not only less clinically effective but also not cost effective. Given the number of prolapse procedures currently performed (28,000 annually in the UK)¹⁴ and the anticipated rise in need for such surgery with an ageing population (a two fold increase in the age group at risk in the next thirty years is predicted)¹⁵ the potential cost implications for the health service are considerable.

1.1 Scale of the problem in the UK and use of NHS resources

Pelvic organ prolapse (POP) is the descent from its normal anatomical position of some of the female genital organs. POP is caused by herniation through deficient pelvic fascia, or due to weaknesses or deficiencies in the ligaments or muscles which should support the pelvic organs. There is little epidemiological research into this condition because it has a variety of presentations and they do not all cause symptoms, particularly in the early stages. ¹⁶ Estimates of the prevalence of prolapse vary from 41% ¹⁷ to 50% ¹⁸ of women over the age of 40 years.

It has been estimated that women have a lifetime risk of 11% of undergoing surgery for urinary incontinence or prolapse and 7% for prolapse alone. The annual incidence of surgery for POP is within the range 15 to 49 cases per 10,000 women years, and it is likely to double in the next 30 years. Little is known about the prevalence and effectiveness of different types of operations, but it is notoriously prone to failure: around 30% of women undergo further operations, the mean time interval to the first secondary operation is about 12 years, and the time interval between subsequent procedures decreases with each successive repair. In addition, repair of one type of prolapse may predispose the women to the development of a different type of prolapse (a new, or de novo prolapse) in another compartment of the vagina due to alteration in the dynamic forces within the pelvis.

Surgery is common. In England and Wales in 2004-2005, 26,947 women were admitted to hospital with a main diagnosis of female genital prolapse, and 28,297 operations were performed (some women had more than one type of prolapse operation). The majority of the operations (93%) were in women having anterior repair (n=8,560), posterior repair (5,406), or both operations (5,654), or with a concomitant uterine prolapse (6,837). Only 7% were in women with vault prolapse (1,840). Assuming a population of about 20 million women in the age group at risk for prolapse surgery (50 to 85 years), the UK operation rate is currently around 14¹⁴ to 16²⁰ women having prolapse operations per 10,000 per year.

The need is likely to increase due to the rising number of elderly women. It has been projected that the number of women in the age group 50 to 85 years (those most likely to need prolapse surgery) will increase by 1.14 million between 2004 and 2014.¹⁵

1.2 The decision to test alternative forms of surgery Existing research

There is little evidence available from RCTs to guide management for women with prolapse. Three Cochrane reviews cover the main options: surgical management;¹ and conservative management including: mechanical devices;² and physical treatment such as pelvic floor muscle training (PFMT).³ A new Interventional Procedures (IP) review has also just been published on the use of mesh in anterior and posterior prolapse surgery.⁴

1.2.1 Conservative management for women with prolapse

Although there are no RCTs to guide the use of mechanical devices (pessaries or rings),² these are often used for women who are unfit for surgery or who wish to avoid surgery. They can be very efficacious, but questions remain about the best type of device, the long term adverse effects and the use of supplementary treatment such as oestrogen. Further research is required. Conservative physical treatments such as PFMT are also often recommended as first line management. A recent update of the relevant Cochrane review³ has found three small and inconclusive trials, suggesting that further research is required. A multicentre RCT is under way in the UK to address this evidence gap (the POPPY trial, Pelvic Organ Prolapse PhysiotherapY).

1.2.2 Surgical management for women with anterior or posterior vaginal wall prolapse

A new update of the Cochrane Review of surgery for prolapse¹ identified 13 RCTs of surgical interventions for women with anterior or posterior pelvic organ prolapse. The IP review⁴ for NICE has identified a further nine RCTs which are not yet included in the Cochrane review. The total number of women receiving mesh in the IP systematic review⁴ was 4569: mesh was inserted using an introducer device, trochar or kit in 503 of these women. There were no data on the differential effects in women having primary as opposed to secondary surgery: all the trials reported both groups of women together despite their potentially different prognoses.

Differences in inclusion criteria or interventions (e.g. types of women, operations or mesh) precluded much useful meta-analysis or reliable conclusions. There were two small but inconclusive RCTs comparing standard repairs with or without mesh with site specific fascial defect repairs^{22;23}. There were another two small and inconclusive RCTs which included a mesh introducer device arm. ^{24;25}

For anterior vaginal wall prolapse, the limited RCT data from the Cochrane review¹ and the IP review⁴ (9 RCTs) suggested that any mesh might reduce subsequent objective anatomical relapse (77/557, 14% relapse) compared with using no mesh (179/591, 30%) (RR 0.48, 95% CI 0.32 to 0.72) in the short term. The IP review⁴ also included additional data from non-randomised comparative studies and case series. Using these extra data, non-absorbable synthetic mesh had the lowest failure rate:

- compared with absorbable synthetic mesh (OR adjusted for bias from study design 0.23, 95% CI 0.12 to 0.44);⁴ and
- compared with absorbable biological mesh (OR adjusted for bias from study design 0.37, 95% CI 0.23 to 0.59).⁴

On the other hand, the mesh erosion rates increased from 1% (95% CI 0.1% to 4%) with synthetic absorbable mesh to 6% with absorbable biological mesh to 10% with non-absorbable synthetic mesh.⁴ The data were too sparse, however, for other

reliable statistical analysis. There were insufficient data on women's subjective prolapse symptoms or complications such as infection, blood loss or dyspareunia, and none on long term outcomes. Particular safety worries are related to the use of introducer devices (trochars) that are needed for the blind insertion of mesh into intra-pelvic spaces.²⁶

These and other findings were presented to the Interventional Procedures Advisory Committee (IPAC) in January 2008, and their guidance has now been published: http://www.nice.org.uk/guidance/index.jsp?action=byID&o=11363. The Committee recommended that mesh should only be used under special arrangements for clinical governance, consent and audit or research.

